9.4.3. Laboratory Tests

For each patient, laboratory tests detailed in ([Appendix 2](#)) should be conducted according to the Schedule of Activities (Section 2). Flexibility in blood sample collection is allowed where blood sample volume restrictions may apply; refer to protocol [Appendix 13](#).

Use of local anesthetics (e.g., EMLA cream) consistent with local prescribing information are permitted during the study visit to ease discomfort associated with venipunctures. Home visits to collect blood and urine samples may be allowed upon written approval from the sponsor and if consistent with local regulations.

Alkaline phosphatase laboratory results may be out of the normal range in pediatric patients because of normal bone growth processes, and collection of a blood sample for bone alkaline phosphatase may be requested by the Sponsor as a reflex test if the alkaline phosphatase result is high.

With the exception of laboratory test results that may unblind the study, Lilly or its designee will provide the investigator with the results of laboratory tests analyzed by a central vendor, if a central vendor is used for the clinical trial.

Any clinically significant findings from laboratory tests that result in a diagnosis and that occur after the patient receives the first dose of IP should be reported to Lilly or its designee as an AE via CRF/electronic data entry / designated data transmission methods.

Fasting Laboratory Tests:

Recommended fasting times by age and weight are as follows:

- Adolescents ≥ 12 years: fast for 12 hours prior to laboratory test
- Children 8 to < 12 years and weighing > 50 kg: fast for 12 hours prior to laboratory test
- Children 8 to < 12 years and weighing ≤ 50 kg: fast for 8 hours prior to laboratory test
- Children < 8 years and weighing 25 to ≤ 50 kg: fast for 8 hours prior to laboratory test
- Children < 8 years and weighing 10 to ≤ 25 kg: fast for 6 hours prior to laboratory test
- Children < 8 years and weighing < 10 kg: fast for 4 hours prior to laboratory test

Urinalysis:

If an urinalysis sample is unable to be collected in younger children, particularly those who have not been toilet trained, this will not be considered to be a protocol violation provided that the site maintains appropriate documentation of why the sample is missing.

9.4.4. Physical Exam

For each patient, a complete physical examination (excluding pelvic and rectal examinations) will be performed at Visit 1 (Screening). A symptom-directed physical examination will be performed at other visits as specified in the Schedule of Activities (Section 2). A complete physical examination may be repeated at the investigator's discretion at any time a patient presents with physical complaints.

9.4.4.1. Tanner Stage Scale

The Tanner Stage Scales are a series of line drawings that are designed to assess sexual maturity of the patient, and will be included as a baseline assessment. The line drawings are intended for patient self-assessment; however, this assessment may be also conducted by an appropriate health care professional if the patient and legal guardian agree (Marshall and Tanner 1969, 1970; Tanner and Davies 1985; Chavarro et al. 2017). Assessment by the health care professional will not be completed if the patient and parent do not provide appropriate consent and assent. The self-assessment will only be collected if the appropriate translation of the scale is available for use at the time of the baseline assessment.

9.4.5. Columbia Suicide Severity Rating Scale

The Columbia Suicide Severity Rating Scale (C-SSRS) captures the occurrence, severity, and frequency of suicidal ideation and/or behavior during the assessment period. The C-SSRS will only be collected in patients ≥ 7 years old. A children's version of the C-SSRS will be completed for patients 7 to < 12 years old, and an adolescent/adult version of the C-SSRS will be completed

for patients 12 to <18 years old. The scale includes suggested questions to solicit the type of information needed to determine if suicidal ideation and/or behavior occurred. The C-SSRS is administered by qualified site personnel. The tool was developed by the National Institute of Mental Health trial group for the purpose of being a counterpart to the Columbia Classification Algorithm of Suicide Assessment categorization of suicidal events. For this study, the scale has been adapted (with permission from the scale authors) to include only the portion of the scale that captures the occurrence of the 11 preferred ideation and behavior categories. The nonleading AE collection should occur prior to the collection of the C-SSRS. If a suicide-related event is discovered *during the C-SSRS* but was not captured during the nonleading AE collection, sites should not change the AE form. If an event is serious or leads to discontinuation, this is an exception where the SAE and/or AE leading to discontinuation should be included on the AE form and the process for reporting SAEs should be followed.

9.4.6. Self-Harm and Follow-Up Supplement Forms

Suicide-related events (behavior and/or ideations) will be assessed and evaluated at every visit with the administration of the C-SSRS and the Self-Harm Supplement Form. The Self-Harm Supplement Form is a single question to enter the number of suicidal behavior events, possible suicide behaviors, or nonsuicidal self-injurious behaviors. If the number of behavioral events is greater than zero, it will lead to the completion of the self-harm follow-up form. The self-harm follow-up form is a series of questions that provides a more detailed description of the behavior cases.

9.4.7. Tuberculosis Testing

Patients will be tested at screening (Visit 1) for evidence of active or latent TB as described in the exclusion criteria (Section 6.2). Investigators should follow local guidelines for monitoring.

9.4.8. Hepatitis B Virus DNA Monitoring

Patients who are HBcAb positive and HBV DNA negative (undetectable) at Visit 1 will require measurement of HBV DNA per the Schedule of Activities, regardless of their hepatitis B surface antibody (HBsAb) status.

The following actions should be taken in response to HBV DNA test results:

- If a single result is obtained with a value “below limit of quantitation,” the test should be repeated within approximately 2 weeks. If the repeat test result is “target not detected,” HBV DNA monitoring will be performed per study schedule (Section 2).
- If the patient has 2 or more test results with a value “below limit of quantitation” or a test result above the limit of quantitation, the patient will be permanently discontinued from IP (see Section 8.1.2) and should be referred to a hepatology specialist.

9.4.9. Safety Monitoring

Lilly will periodically review evolving aggregate safety data within the study by appropriate methods.

In the event that safety monitoring uncovers an issue that needs to be addressed by unblinding at the group level, only members of the data monitoring committee (an advisory group for this study formed to protect the integrity of data; refer to Interim Analyses section [Section 10.3.8]) can conduct additional analyses of the safety data.

The Lilly CRP will monitor safety data throughout the course of the study. Lilly will review SAEs within time frames mandated by company procedures. The Lilly clinical research physician will, as is appropriate, consult with the functionally independent Global Patient Safety therapeutic area physician or clinical scientist and periodically review trends in safety data and laboratory analytes. Any concerning trends in frequency or severity noted by an investigator and/or Lilly (or designee) may require further evaluation.

All deaths and SAE reports will be reviewed in a blinded manner by Lilly during the clinical trial. These reports will be reviewed to ensure completeness and accuracy but will not be unblinded to Lilly during the clinical trial. If a death or a clinical AE is deemed serious, unexpected, and possibly related to IP, only Lilly Global Patient Safety will be unblinded for regulatory reporting and safety monitoring purposes. These measures will preserve the integrity of the data collected during this trial and minimize any potential for bias while providing for appropriate safety monitoring.

Investigators will monitor vital signs and carefully review findings that may be associated with cardiovascular and venous thrombotic events. Adverse event reports and vital signs will be collected at each study visit. The cardiovascular monitoring plan includes the following:

- regular monitoring of lipid levels
- potential MACE (cardiovascular death, MI, stroke), other cardiovascular events (such as hospitalization for unstable angina, hospitalization for heart failure, serious arrhythmia, resuscitated sudden death, cardiogenic shock, coronary revascularization such as coronary artery bypass graft or percutaneous coronary intervention), venous and arterial thrombotic events, and noncardiovascular deaths will be identified by the investigative site or through medical review and will be sent to a blinded Clinical Event Committee for adjudication at regular intervals.

9.4.9.1. Hepatic Safety Monitoring

If a study patient experiences elevated ALT $\geq 3X$ upper limit of normal (ULN), alkaline phosphatase (ALP) $\geq 2X$ ULN (for patients with baseline $< 2x$ ULN), or elevated TBL $\geq 2X$ ULN, liver testing ([Appendix 4](#)) should be repeated within 3 to 5 days including ALT, AST, ALP, TBL, direct bilirubin, gamma-glutamyl transferase, and creatine kinase to confirm the abnormality and to determine if it is increasing or decreasing. If the abnormality persists or worsens, clinical and laboratory monitoring should be initiated by the investigator and in consultation with the study medical monitor. Monitoring of ALT, AST, TBL, and ALP should continue until levels normalize or return to approximate baseline levels.

Hepatic Safety Data Collection

Additional safety data should be collected via the case report form (CRF) or other designated data transmission methods if 1 or more of the following conditions occur:

- elevation of serum ALT to $\geq 5X$ ULN on 2 or more consecutive blood tests
- elevated serum TBL to $\geq 2X$ ULN (except for cases of known Gilbert's syndrome)
- elevation of serum ALP to $\geq 2X$ ULN on 2 or more consecutive blood tests (for patients with baseline $< 2x$ ULN)
- patient discontinued from treatment due to a hepatic event or abnormality of liver tests
- hepatic event considered to be a SAE

9.4.9.2. Venous Thromboembolic Event Assessment

If a patient develops the clinical features of a deep vein thrombosis or pulmonary embolism, appropriate local laboratory tests and imaging are recommended, as necessary, for diagnosis of the event. For confirmed cases, additional laboratory testing should be performed as outlined in [Appendix 5](#). All suspected VTE events will be independently adjudicated by an external blinded Clinical Event Committee.

9.4.9.3. Growth Monitoring

Height and weight, left hand x-rays, knee x-rays, hormone levels, and occipital frontal circumference will be collected as described below and according to the Schedule of Activities (Section 2) to allow for the identification of potential effects on growth and development:

- Height measurements will be made using a stadiometer. Height measurements must be recorded to 1 decimal place without rounding.
- Weight measurements must be recorded to 1 decimal place without rounding.
- Instruments used for measuring height and weight should be appropriately and regularly calibrated.
- All measurements of height and weight should be made without shoes and after the removal of any heavy personal items (that is, large jewelry, wallets, coats, etc.).
- Height and weight changes in pediatric patients (both at an individual and group level) will be reviewed by the DMC external to Lilly.
- Left hand x-rays will be collected to assess effects on bone age.
 - Ongoing patients will have hand x-rays completed approximately every 6 months per the Schedule of Activities (Section 2) after approval of this protocol amendment and completion of the consent form. A central vendor will be used for reading of the x-ray images.
- Knee x-rays will be collected to monitor bone growth.

- An x-ray of the knee (anteroposterior) will be collected approximately every 6 months as shown in the Schedule of Activities (Section 2). A central vendor will be used for reading of the x-ray images.
- Ongoing patients will have a knee x-ray at the next scheduled visit after approval of this protocol amendment and completion of the consent form. Subsequent knee x-rays will be collected per the Schedule of Activities (Section 2), unless the subsequent visit is within 3 months of the first knee x-ray, in which case the knee x-ray can be skipped at this timepoint to avoid unnecessary radiation exposure.
- If a local addendum is in place that specifies another mode of imaging (e.g., magnetic resonance imaging [MRI] instead of x-ray), the local addendum should be followed. Otherwise, the current protocol amendment should be followed with regard to knee x-rays.
- Any symptomatic areas of bones/joints will be assessed and investigated as appropriate by study investigators. Any diagnoses made based on symptomatic areas of bones/joints or imaging data will be reported as appropriate (e.g., recorded on eCRF).
- Biomarkers that will be collected to provide information on bone health include: ALP and calcium (collected as part of the clinical chemistry panel).
- Insulin-like growth factor (IGF)-1, the principal mediator of growth hormone, and IGF-binding protein (IGF-BP)-3, the principal carrier protein for IGF-1, will be collected for the assessment of growth-related disorders.
- Gonadal hormones (estradiol for females or testosterone for males) will be collected for the assessment of pubertal development in patients 8 to <18 years of age.

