	Updated the section to align with the changes in the main body of the protocol	For consistency
2. Schedule of Activities 4. Objectives and Endpoints 5.1. Overall Design 5.1.3. Period 3: Double-blind Placebo-Controlled Treatment Period 5.1.4. Period 4: Long-term Extension Treatment Period 5.1.5. Period 5: Post-Treatment Follow-up 10.3.3.3. Tertiary/Exploratory Analyses	Extended Study Period 4 by up to an additional 1 year for patients for whom a systemic JAK or biologic treatment is not available	This extension of treatment will allow for continued efficacy and safety data collection and will allow patients to continue to receive baricitinib treatment for up to an additional 1 year until baricitinib is commercially available for the population or not approved.
2. Schedule of Activities 7.7.2. Use of Topical Corticosteroids	Defined that sponsor will provide low- and moderate-potency TCS through study Visit 27. At Visit 28 and beyond, sponsor will not provide TCS.	This will allow use of TCS products that are preferred by the patient and are locally available to the patient upon study completion.
2. Schedule of Activities	Defined that the collection of imaging (x-ray, MRI) is not required after the patient reaches 18 years of age	Most patients will have completed growing by 18 years of age. Discontinuing the collection of imaging when growth is not expected will eliminate the risks associated with unnecessary x-ray exposure.

Section # and Name	Description of Change	Brief Rationale
	Revised footnote “a” and added footnote “s”	To align with the additional visits
4. Objectives and Endpoints 10.3.3.3. Tertiary/Exploratory Analyses	Added “Proportion of patients achieving SCORAD75 at 2, 3, 4, and 5 years during long-term extension.” as exploratory objective	To align SCORAD analysis timepoints with IGA and EASI 75 exploratory objectives
9.4.3 Laboratory Tests	Added a statement to refer Appendix 13 as incorporated Protocol Addendum (4) as a new Appendix 13	To avoid country and region-specific protocol versions in the EU
Appendix 11. Additional Procedures for Countries Participating in the PK Lead-in Period (Study Period 2)	Added this new appendix and included the content from PK Addendum (5). Also, updated the SoA as per current protocol amendment	To avoid country and region-specific protocol versions in the EU

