- k Fasting lipid profile: Patients should not eat or drink anything except water for 4 to 12 hours (depending on age and weight as specified in Section 9.4.3) prior to sample collection. If a patient attends these visits in a nonfasting state, this will not be considered to be a protocol violation.
- l Left hand and knee x-rays at an early termination visit is not required if previously taken within 6 months of the early termination visit. The collection of x-rays and other imaging procedures should be discontinued after the patient reaches 18 years of age.
- m Estradiol (for females) or testosterone (for males) will be collected for the assessment of maturation in patients aged 8 to <18 years.
- n Pregnancy tests prior to first dose of investigational product for females ≥ 10 years old of age (<10 years at investigator discretion) if menarche reached or if there is reason to believe the patient is sexually active. Pregnancy test results from Visit 2 must be known prior to first dose of investigational product. A serum pregnancy test (central laboratory) will be performed at Visit 1. Urine pregnancy tests (local laboratory) will be performed at Visit 2 and at all subsequent study visits after Visit 3. If required per local regulations and/or institutional guidelines, pregnancy testing can occur at other times during the study treatment period.
- o For patients who are positive for HCV antibody, a follow-up test for HCV RNA will be performed automatically. Patients who are positive for HCV antibody and negative for HCV RNA may be enrolled.
- p Patients who are positive for hBcAb and negative for HBV DNA may be enrolled. Any enrolled patient who is HBcAb positive, regardless of hBsAb status or level, must undergo HBV DNA testing per the schedule (see Section 9.4.8).
- q At Visit 2 all laboratory samples, with the exception of PK samples, will be obtained prior to the first dose of IP.
- r PK samples will be collected as described in Section 9.5.
- s At Visit 27, patients should be discontinued from study treatment and begin study discontinuation procedures unless sponsor's written approval is obtained to allow the patient to continue on study treatment. Refer to Section 5.1.4.

Table JAIP.2. Schedule of Activities for Patients Randomized to Double-blind Treatment in Study Period 3

	Screening	Double-blinded Treatment							Long-term Extension Treatment										
	Period 1	Period 3							Period 4										

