- k Fasting lipid profile: Patients should not eat or drink anything except water for 4 to 12 hours (depending on age and weight as specified in Section 9.4.3) prior to sample collection. If a patient attends these visits in a nonfasting state, this will not be considered to be a protocol violation.
- l Left hand and knee x-rays at an early termination visit is not required if previously taken within 6 months of the early termination visit. The collection of x-rays and other imaging procedures should be discontinued after the patient reaches 18 years of age.
- m Estradiol (for females) or testosterone (for males) will be collected for the assessment of maturation in patients aged 8 to <18 years.
- n Pregnancy tests prior to first dose of investigational product for females ≥ 10 years old of age (<10 years at investigator discretion) if menarche reached or if there is reason to believe the patient is sexually active. Pregnancy test results from Visit 2 must be known prior to first dose of investigational product. A serum pregnancy test (central laboratory) will be performed at Visit 1. Urine pregnancy tests (local laboratory) will be performed at Visit 2 and at all subsequent study visits after Visit 3. If required per local regulations and/or institutional guidelines, pregnancy testing can occur at other times during the study treatment period.
- o For patients who are positive for HCV antibody, a follow-up test for HCV RNA will be performed automatically. Patients who are positive for HCV antibody and negative for HCV RNA may be enrolled.
- p Patients who are positive for hBcAb and negative for HBV DNA may be enrolled. Any enrolled patient who is hBcAb positive, regardless of hBsAb status or level, must undergo HBV DNA testing per the schedule (see Section 9.4.8).

- q At Visit 2 all laboratory samples, with the exception of PK samples, will be obtained prior to the first dose of IP.
- r PK samples will be collected as described in Section 9.5.
- s At Visit 27, patients should be discontinued from study treatment and begin study discontinuation procedures unless sponsor's written approval is obtained to allow the patient to continue on study treatment. Refer to Section 5.1.4.

3. Introduction

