Appendix 14. Protocol Amendment History

The Protocol Amendment Summary of Changes Table for the current amendment is located directly before the Table of Contents (TOC).

Amendment [b]: (06-Aug-2020)

Overall Rationale for the Amendment

Protocol I4V-MC-JAIP - A Phase 3, Multicenter, Randomized, Double-blind, Placebo-controlled, Parallel-group, Outpatient Study Evaluating the Pharmacokinetics, Efficacy, and Safety of Baricitinib in Pediatric Patients with Moderate-to-Severe Atopic Dermatitis- has been amended. The new protocol is indicated by amendment (b) and will be used to conduct the study in place of any preceding version of the protocol.

The overall changes and rationale for the changes made to this protocol are described in the following table. Editorial revisions with no impact on protocol design or implementation were also made. These revisions are not noted in this protocol amendment summary except where contained in a section with substantive changes.

There are 3 main changes incorporated into this protocol amendment:

- Addition of knee imaging and increased frequency of hand x-ray requirements related to monitoring bone growth and clarification of assessment of any symptomatic areas of bones/joints were included based on regulatory feedback. In addition, baseline assessment of sexual maturation was included based on regulatory feedback.
- Extension of the duration of treatment for all patients.
- Guidance for study implementation under exceptional circumstances, such as pandemics or natural disasters.

Amendment Summary for Protocol I4V-MC-JAIP Amendment (b)

Section # and Name	Description of Change	Brief Rationale

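### Section 9.4.9.3 orders a knee x-ray at the next visit for ongoing patients without excepting children under 18 already on the 6-monthly knee series, so some would have a film about 12 weeks after the last

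*Protocol*

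**What the plan says.** Section 9.4.9.3 (Growth Monitoring) first sets the routine: "An x-ray of the knee (anteroposterior) will be collected approximately every 6 months as shown in the Schedule of Activities (Section 2"). It then adds a rule for patients already in the study: "Ongoing patients will have a knee x-ray at the next scheduled visit after approval of this protocol amendment and completion of the consent form". Later knee films follow the schedule, "unless the subsequent visit is within 3 months of the first knee x-ray, in which case the knee x-ray can be skipped".

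The matching rule for hand films is tied to the schedule: "Ongoing patients will have hand x-rays completed approximately every 6 months per the Schedule of Activities (Section 2) after approval of this protocol amendment".

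The knee row in Tables JAIP.1 and JAIP.2 sends sites to Section 9.4.9.3 for ongoing patients. Footnote l to both tables adds an age limit, "The collection of x-rays and other imaging procedures should be discontinued after the patient reaches 18 years of age", and waives hand and knee films at an early termination visit if they were taken in the previous 6 months. Section 9.4.9.3 also lets a local addendum that names another imaging mode take precedence.

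Appendix 14 lists among the main changes of amendment (b), dated 06-Aug-2020: "Addition of knee imaging and increased frequency of hand x-ray requirements related to monitoring bone growth". The summary of changes for amendment (c) explains its own age limit on imaging: "Discontinuing the collection of imaging when growth is not expected will eliminate the risks associated with unnecessary x-ray exposure".

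**The concern.** Knee imaging came in with amendment (b), so children followed under (b) should already be on the 6-monthly series when (c) takes effect. The knee sentence sets no condition on earlier films. It is tied to whichever visit comes next, whether or not that visit carries a film. The hand sentence uses the same reference to the amendment but does no harm, because it only repeats the schedule.

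None of the stated limits exempts a child under 18 on the series. The age limit and the addendum clause concern other patients. The early-termination waiver concerns one type of visit. The skip clause acts on later films and is optional.

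At stake is a paediatric x-ray with no stated purpose at that time, in a protocol whose current amendment sets out to reduce needless exposure. A site that sensibly leaves the film out departs from the text.

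**Working it through.** **Inputs.** Visit weeks come from Tables JAIP.1 and JAIP.2.

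- PK lead-in (Table JAIP.1): knee films at Visits 12, 14, 16, ..., 30 (Weeks 28, 52, 76, ..., 244).
- Randomized (Table JAIP.2): knee films at Visits 21, 23, ..., 31 in the extended table. For Visits 13, 15, 17 and 19 I used the same alternate-visit pattern, which agrees with the knee imaging row in Appendix 12.3. The text copy of the first part of Table JAIP.2 sets this row one column to the left; I took that as a reading artefact.

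**The plan's own interval.** In the regular part of both schedules, films are 24 weeks apart: 24 × 7 = 168 days, or 168 / 30.4375 = 5.5 months. This reproduces the stated 6 months approximately.

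**Visits where the literal rule adds a film.** I count from Visit 13, where alternation is regular in both schedules: 31 − 13 + 1 = 19 visits.

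| Group | Film visits | Visits without a film |
|---|---|---|
| PK lead-in | 14, 16, ..., 30 (9) | 13, 15, ..., 31 (10) |
| Randomized | 13, 15, ..., 31 (10) | 14, 16, ..., 30 (9) |

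At each visit without a film, the last film was 12 weeks earlier, half the 24-week spacing. That is 84 days nominally. With ±7 days at both visits it is 84 ± 14, or 70 to 98 days. Earlier randomized visits are irregular: with a film at Week 24, Visit 11 is 4 weeks after it and Visit 12 is 16 weeks after it.

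**Effect on the number of films.** Weeks 100, 124 and 148 carry films in both schedules.

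- As scheduled: 3 films.
- Film added at Week 112, skip not used: 3 + 1 = 4.
- Film added at Week 112, Week 124 skipped: 3 + 1 − 1 = 3. The next film follows after 148 − 112 = 36 weeks.

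In general the change is +1 without the skip. With the skip it is 0 if a later scheduled film exists. One does exist for all 9 randomized positions and for 9 of the 10 PK lead-in positions, through Visit 31. The exception is PK lead-in Visit 31 (Week 256), after which no film is scheduled. The 36-week gap arises only where a further film follows the skipped one.

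**Whether the skip is available.** If the film it refers to is the added one, the next scheduled film comes 84 + b − a days later, with a and b each between −7 and 7. Taking 3 months as 91 days, it is too late when b − a is 8 or more: 7 + 6 + 5 + 4 + 3 + 2 + 1 = 28 of 15 × 15 = 225 day pairs. If visit days were spread evenly over the windows (an assumption), the skip would be open in 197/225 = 88% of cases. If the clause means the child's actual first knee film, it would not apply to a child whose series began long before, and the extra film stands.

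**PK lead-in patients stopping at Visit 27 (Week 208).** Footnote s says "At Visit 27, patients should be discontinued from study treatment and begin study discontinuation procedures", unless the sponsor agrees otherwise in writing. The last film was at Visit 26 (Week 196), 12 weeks before. Footnote a calls for an early termination visit when a patient leaves before Visit 31, so the 6-month waiver in footnote l arguably removes the added film. A scheduled completion at Visit 31 is less clearly covered.

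**The case against.** The strongest reply is that the sentence should be read with its neighbours. The paragraph opens with the 6-monthly rule, and the following sentence calls the resulting film the first knee x-ray and gives avoidance of unnecessary radiation as its aim. That wording fits a patient starting knee imaging, and an experienced site may read it so. This stands as evidence of intent. It does not supply the missing condition, and the schedule sends sites to this very text.

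It is also fair that the skip, if used, usually leaves the number of films unchanged. The effect is then mainly one film moved 12 weeks earlier, not an added exposure. The waiver in footnote l likewise shows that the protocol does not mean to repeat recent films.

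A reader might infer that every ongoing child gets an additional film. The text does not support that. Patients aged 18 or over, sites under a local imaging addendum and children whose next visit already carries a film are unaffected, and the skip offsets most of the rest.

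A reader might also conclude that the sentence is demonstrably left over from amendment (b). That is plausible, since (b) introduced knee imaging and no visible entry in the (c) change table names Section 9.4.9.3. But the (b) text of the section is not available and the visible change table is incomplete, so it remains an inference. The defect does not depend on it.

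**Conclusion.** The instruction is wrong as written, and the matter is minor. For a child under 18 already on the knee series whose next visit has no scheduled film, literal compliance puts a film about 12 weeks (70 to 98 days) after the last. The cost is at most one extra film per child. Often it is no extra film, but a displaced series with one 36-week gap. The clearest case that cannot be offset is a PK lead-in patient whose next visit is Visit 31.

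The visit counts show where the rule bites; they are not shares of patients. The protocol does not say where patients stood in the schedule when (c) was approved, so the number affected is unknown. The result rests on a literal reading and on the nominal visit weeks. No efficacy, growth or bone-age endpoint changes. For an ongoing child with no knee image yet, the sentence still serves a purpose and should stay.

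**What to change.** Limit the sentence in Section 9.4.9.3 to ongoing patients under 18 with no prior on-study knee image, whatever the reason. State that all other ongoing patients continue knee x-rays per the Schedule of Activities, as the hand x-ray sentence already does. The cost is one sentence. No scheduled film or data are lost, and children who still lack a knee image keep their catch-up film.
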